Randomisation will occur after the participant has provided informed consent 72 hours before the surgical procedure is due to start. Participants are randomised to a treatment group in a 1:1 ratio using a computer-generated dynamic procedure (minimisation) with a random component. Minimisation variables are trial centre, surgical procedure category (surgery involving the gut and all other surgery) and ACE-I and/or ARB category. Each participant will be allocated with 80% probability to the treatment group that minimises between group differences in these factors among all participants recruited to the trial to date, and to the alternative group with 20% probability. To enter a patient into the SPACE trial, research staff at the site will log on to a secure web-based randomisation and data entry platform hosted by Queen Mary University of London and complete the patient's details to obtain a unique patient identification number and allocation to a treatment group. A patient's treatment group allocation will only be revealed to the person performing randomisation.

5. Analysis methods

General analysis principles

Analyses will follow the intention-to-treat principle: all randomised patients with a recorded outcome will be included in the analysis and analysed according to the treatment to which they were randomised [3, 4]. Patients will be included in the analysis, regardless of whether the treatment they received was compliant with the protocol. Definitions of what constitutes a recorded outcome for each outcome can be found in Appendix 1. Patients with missing outcome data will be excluded from the analysis. Missing data for baseline covariates to be included in the analysis model will be accounted for using mean imputation for continuous variables and the missing indicator approach will be used for missing data for categorical variables [5, 6].

For the analysis of the primary outcome, each secondary outcome, and all process measures, we will present the following information:

- The number of patients included in each analysis, by treatment group
- A summary statistic of the outcome (e.g. mean (SD), number (%)), by treatment group
- The estimated treatment effect
- A 95% confidence interval for the estimated treatment effect
- A two-sided p-value

For all analyses, a significance level of 5% will be used.

Representativeness of patients

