The primary outcome, myocardial injury within 48 hours after surgery, will be analysed using a mixed-effect logistic regression model, with a random intercept for the minimisation variable trial centre [8]. The model will be adjusted for minimisation variables as fixed factors which are planned surgical procedure ((a) surgery involving the gut; (b) all other surgery) and class of drug routinely taken ((a) ACE-I; (b) ARB) [9]. The model will also be adjusted for the following pre-specified baseline covariates [10-12]: age and gender (M/F). All covariates will be entered into the model as fixed factors. Age will be included as a continuous variable, assuming a linear association with the outcome [13].

When participants are randomised according to incorrect baseline information, under the ITT principle they should be analysed in their allocated treatment group, irrespective of the fact that their allocation was based on incorrect information. The incorrect baseline information should be kept in the randomisation record, as this reflects how the randomisation was performed, and the correct information documented for use in an adjusted analysis [14].

Analysis of secondary outcomes

Peak level of Troponin-T measured within 48 hours of surgery

The mean (SD) peak level of Troponin-T measured within 48 hours of surgery will be reported within each treatment group. Differences between the groups in the mean peak level troponin-t will be analysed using multilevel linear regression – adjusted for the same baseline variables as the adjusted analysis of the primary outcome. We will also adjust for baseline pre-operative Troponin-T as a continuous variable.

Infection within 30 days of surgery

Infection within 30 days of surgery will be analysed using a mixed-effect logistic regression model with a random intercept for the minimisation variable trial centre. The model will be adjusted for minimisation variables planned surgical procedure ((a) surgery involving the gut; (b) all other surgery) and class of drug routinely taken ((a) ACE-I; (b) ARB).

The expected event rate for this outcome is low, and as such we have reduced the number of covariates included in the model to avoid over-stratification.

Myocardial infarction within 30 days of surgery

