The number (%) will be presented in each treatment group. An exact unadjusted logistic regression will be performed if 10 or more events are reported. No statistical analysis will be performed if there are fewer than 10 events.

Acute heart failure within 30 days of surgery

The number (%) will be presented in each treatment group. An exact unadjusted logistic regression will be performed if 10 or more events are reported. No statistical analysis will be performed if there are fewer than 10 events.

Stroke within 30 days of surgery

The number (%) will be presented in each treatment group. An exact unadjusted logistic regression will be performed if 10 or more events are reported. No statistical analysis will be performed if there are fewer than 10 events.

Death within 30 days of surgery

The number (%) will be presented in each treatment group. An exact unadjusted logistic regression will be performed if 10 or more events are reported. No statistical analysis will be performed if there are fewer than 10 events.

Strategy for analysis of primary and secondary outcomes if model fails to converge

If the statistical models for any of the primary or secondary outcomes do not converge, then the following steps will be taken:

- 1. The model will be fitted without a random intercept for trial centre
- 2. As above, but excluding any additional covariates apart from minimisation variables
- 3. As above, but also excluding minimisation variables.

Plan in case of over-stratification

When adjusting for covariates in the primary analysis or secondary analysis models where the outcome is binary, if there is a category within that covariate where no events have occurred in either of the treatment groups, the statistical model will exclude all patients within this category. To overcome this, this category will be merged with another category; this will be decided by the chief investigator who will be blinded to results. This will apply to covariates with three or more categories. However, if all but one category within that covariate have no events recorded in one of the treatment groups then we will exclude this covariate from the model.

Sensitivity analysis

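### If a model fails to converge, the first fallback step removes trial centre, a minimisation factor, with nothing in its place; the loss is contingent and fixed centre terms would avoid it

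*SAP*

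**What the plan says.** SAP section 4, Randomisation procedure, names three balancing factors: "Minimisation variables are trial centre, surgical procedure category (surgery involving the gut and all other surgery) and ACE-I and/or ARB category". Allocation is strongly steered by them: "Each participant will be allocated with 80% probability to the treatment group that minimises between group differences in these factors".

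SAP section 5, Primary analysis, puts centre into the model as a random intercept and the other two factors as fixed effects, then adds age and gender. The peak-troponin model uses the same adjustment plus baseline troponin. The infection model has the random intercept and the two fixed minimisation factors only. Myocardial infarction, heart failure, stroke and death are analysed without adjustment.

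The fallback sequence for non-convergence, also in section 5, has three steps:

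- Step 1: "The model will be fitted without a random intercept for trial centre".
- Step 2: "As above, but excluding any additional covariates apart from minimisation variables".
- Step 3: the minimisation variables go as well.

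No step puts a fixed centre term in place of the random intercept.

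**The concern.** The sequence appears designed to give up minimisation factors last, because step 2 protects them explicitly. Yet centre is one of them, its only place in the models is the random intercept, and step 1 has already removed it. In the primary and peak-troponin models it goes while age and gender, which played no part in allocation, stay. Step 2 then protects a set of variables that is no longer complete. The SAP itself cites a paper on improper analysis of minimised trials (reference 9) in support of adjustment.

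Balancing on a factor lowers the true variability of the treatment estimate. A model that omits the factor does not credit that reduction, so its standard error is too large for the estimator it describes. The test is then conservative and power is lost. In a logistic model, omitting a prognostic factor also pulls the odds ratio towards 1.

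**Working it through.** **1. The plan's own figure.** Section 4 gives 50% against 30%, 90% power and p<0.05; section 5 makes tests two-sided. With pooled variance and no continuity correction, n per arm = [1.960·√(2·0.4·0.6) + 1.2816·√(0.5·0.5 + 0.3·0.7)]² / 0.2² = (1.358 + 0.869)² / 0.04 = 124. The total is 248, as stated. The design odds ratio is (0.3/0.7)/(0.5/0.5) = 0.43, log odds ratio −0.847.

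**2. Can fixed centre terms be afforded?** Expected primary events are 124·0.5 + 124·0.3 = 62 + 37.2, about 99. Section 5, Baseline characteristics, lists five centres, which need four indicators beside an intercept.

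**3. Which models does the order affect?**

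| Model | Centre removed at step 1 | Age and gender still present |
|---|---|---|
| Primary | yes | yes |
| Peak troponin | yes | yes |
| Infection | yes | not in the model |
| MI, heart failure, stroke, death | no centre term | unadjusted |

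**4. Primary model, simulated.** Inputs from the SAP: five centres, 80/20 minimisation on three factors, the event rates above, and 247 patients (260 × 0.95). Assumptions: centre shares of 35, 25, 20, 10 and 10%, and the between-centre SD on the log-odds scale. There were 6000 trials per setting, all with age and gender in the model. Monte Carlo standard error of a 5% rate is √(0.05·0.95/6000) = 0.3 points.

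| Centre SD | Mean SE / true SD, step 1 | Type I error %, step 1 v indicators | Power %, step 1 v indicators |
|---|---|---|---|
| 0.01 | 0.99 | 4.7 v 4.9 | 89 v 90 |
| 0.3 | 1.00 | 5.1 v 5.4 | 87.9 v 88.4 |
| 0.5 | 1.01 | 4.5 v 4.9 | 86.6 v 88.0 |
| 0.75 | 1.04 | 3.9 v 5.1 | 81.5 v 84.6 |
| 1.0 | 1.08 | 3.2 v 5.2 | 76.9 v 82.7 |

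Power loss is 84.6 − 81.5 = 3.1 points at SD 0.75 and 82.7 − 76.9 = 5.8 points at SD 1.0. No fit with indicators failed. At SD 1.0 the mean log odds ratio is −0.72 at step 1 and −0.89 with indicators, that is, odds ratios of exp(−0.72) = 0.49 and exp(−0.89) = 0.41. A separate simulation of 3000 trials per setting, with 248 patients, gave type I error of 3.9, 3.4 and 3.1% without centre at SD 0.5, 0.8 and 1.1, against 4.6, 4.5 and 5.2% with indicators.

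**5. Conditioning on the likely trigger.** Step 4 drops centre in every trial, but the SAP does so only after a failed fit. A typical cause is a centre variance estimated at zero. In 2000 null trials per setting, the estimate was taken as zero when its score at zero was not positive.

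| Centre SD | Trials at zero, % | Type I error % in those trials, step 1 v indicators |
|---|---|---|
| 0.01 | 74 | 4.7 v 4.8 |
| 0.3 | 38 | 5.2 v 5.4 |
| 0.5 | 16 | 5.3 v 5.9 |
| 0.8 | 6 | 5.1 v 5.1 |
| 1.1 | 2 | 4.4 v 4.4 |

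The last two rows rest on 117 and 45 trials. In a further run, power among zero-variance trials at SD 0.01 was 88.4 v 88.6%. Among the remaining trials it was 81.5 v 85.0% at SD 0.8 and 75.7 v 80.9% at SD 1.1, losses of 3.5 and 5.2 points.

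**6. Linear model of the peak-troponin type.** There were 3000 trials per setting, without age and gender; the ICC is assumed.

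| ICC | Interval width, step 1 / indicators | Type I error %, step 1 v indicators |
|---|---|---|
| 0.01 | 1.004 | 4.9 v 4.9 |
| 0.05 | 1.024 | 4.5 v 4.9 |
| 0.10 | 1.050 | 4.3 v 4.9 |
| 0.20 | 1.111 | 3.3 v 4.9 |

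This agrees with the approximation √(1/(1 − ICC)), which gives 1.005, 1.026, 1.054 and 1.118.

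**The case against.** The best defence is that the rule removes first the term most likely to cause failure, a variance estimated from five centres, and that it is fixed in advance. The planned primary model does adjust for all three minimisation factors. When the estimated variance is zero, the random-intercept model and the step 1 model coincide, so nothing is lost against the planned analysis. The calculations bear this out: zero estimates are common where centres hardly differ and rare where omitting centre would hurt. This limits the size of the problem. It does not settle it, because the sequence applies whatever the cause of failure and does not ask whether centres differ.

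Three stronger readings are tempting and are not supported:

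- **That the fallback necessarily costs power or precision.** The SAP gives no between-centre variation, and up to an SD of 0.5 the excess in the standard error is nil to 1%.
- **That the primary interval becomes wider than it would be with centre terms.** On the log-odds scale it does not: at SD 1.0 and odds ratio 0.43 the mean standard error is 0.273 at step 1 against 0.309 with indicators, because the estimate shrinks. It is too large only against its own sampling variability. The wider interval is real in the linear model alone.
- **That false positives rise.** The error is in the conservative direction.

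It is also fair to say that infection is expected to be uncommon. The SAP trimmed that model's covariates deliberately, and centre indicators there may run into centres without events.

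**Conclusion.** The inconsistency in the text is certain: centre is a minimisation variable, step 1 removes it without a substitute, and step 2 is worded as though all minimisation variables were still present. The order relative to age and gender matters only in the primary and peak-troponin models.

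The consequence depends on two things the SAP does not give: why a fit would fail, and how far centres differ. With a near-zero variance estimate the loss is negligible. With another cause and an assumed SD of about 0.75 to 1.1, type I error is roughly 3 to 4%, power falls by about 3 to 6 points from a design with 90% planned, and the odds ratio moves towards 1. For peak troponin the interval is 0.4 to 11% wider over the assumed ICC range. No probability can be put on reaching that situation. This is a minor defect in a contingency rule, worth correcting because correction is nearly free.

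**What to change.** Reword the fallback sequence:

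1. Replace the random intercept with fixed centre terms (four indicators for five centres). For binary outcomes, merge a centre with no events under the SAP's existing over-stratification rule, which covers covariates with three or more categories.
2. Drop age, gender and any other non-minimisation covariate, where the model contains them.
3. Remove centre.
4. Remove the remaining minimisation variables.

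Step 2 then means what it says.

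The cost is SAP wording and four parameters against about 99 expected primary events. Where centres do not differ, the simulations show essentially no loss (power 90 v 89%, type I error 4.9 v 4.7%, indicators against step 1 as written, at SD 0.01). The one practical burden is the infection outcome, where centres may need merging or step 3 may be reached sooner.

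### The over-stratification rule drops a covariate on zero events in one arm, although the models lose patients only when a level is empty of events (or non-events) in both arms combined

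*SAP*

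**What the plan says.** The rule is in SAP section 5, under the plan in case of over-stratification. Its scope is set by "When adjusting for covariates in the primary analysis or secondary analysis models where the outcome is binary".

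It first names the problem, a category in which "no events have occurred in either of the treatment groups, the statistical model will exclude all patients within this category". The remedy is to merge that category with another. The chief investigator, blinded to results, decides the merge, and the SAP adds: "This will apply to covariates with three or more categories".

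A second instruction follows, with a different trigger: "if all but one category within that covariate have no events recorded in one of the treatment groups then we will exclude this covariate".

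The models it acts on are in the same section. The primary outcome uses a "mixed-effect logistic regression model, with a random intercept for the minimisation variable trial centre", with fixed effects for "planned surgical procedure ((a) surgery involving the gut; (b) all other surgery) and class of drug routinely taken ((a) ACE-I; (b) ARB") and for "age and gender (M/F). All covariates will be entered into the model as fixed factors". Age is continuous. The infection model has the same random intercept and keeps only procedure and drug class, for this reason: "The expected event rate for this outcome is low, and as such we have reduced the number of covariates". Neither model has a treatment-by-covariate interaction.

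**The concern.** The problem and the trigger do not match. The problem is a level with no events in either arm; the trigger is a level with no events in one arm. Without an interaction, a level's coefficient draws on the events of both arms, so a zero in one arm leaves it estimable.

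The mismatch reaches factors that matter. Every listed categorical fixed covariate has two levels, so all but one category means a single level. Merging cannot apply to these covariates unless a missing-indicator level is added, so on the natural reading exclusion is the rule that operates. Two of the three are minimisation factors, and they are the only fixed covariates in the infection model. The SAP's own non-convergence strategy, just above, gives up minimisation factors only at its third and last step. This rule would give one up at once, from a model that fits.

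**Working it through.** **Inputs.** From the SAP: 1:1 allocation; 248 evaluable patients; primary event rates of 50% (stop) and 30% (continue); two-level covariates; infection rate described only as low. Assumed, because the SAP gives neither: the infection rate and the share of patients in each level.

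**1. Arm size.** Comparing 50% with 30% at two-sided 5% and 90% power (pooled variance, no continuity correction) needs 124 per arm, or 248 in total. This reproduces the SAP's figure, which is not in dispute.

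**2. Does a zero in one arm break the model?** Main-effects logistic fits, fixed part only. Cells are events/patients for level A, then level B.

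| Table | Stop | Continue | Treatment log-OR (SE) | Covariate log-OR (SE) | Treatment log-OR (SE), factor dropped |
|---|---|---|---|---|---|
| Zero in one arm | 20/100, 4/24 | 15/100, 0/24 | -0.562 (0.359) | -0.854 (0.556) | -0.556 (0.357) |
| Zero in one arm, strong factor | 8/62, 2/62 | 6/62, 0/62 | -0.567 (0.543) | -2.06 (0.77) | -0.545 (0.533) |
| Zero in both arms | 20/100, 0/24 | 15/100, 0/24 | – | about -28 (about 460,000) | – |

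The first two fits converge and keep all 248 patients. The third does not converge: level B has no events at all. In addition, 7,021 simulated tables with a level empty of events in exactly one arm all gave finite estimates. The second table also shows that a strongly prognostic factor can be the one removed.

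**3. How often would each condition arise for infection?** For a level with n patients per arm and the same event rate r in both arms:

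- p0 = (1 − r)^n is the chance of no events in one arm
- P(zero in exactly one arm) = 2·p0·(1 − p0)
- P(zero in both arms) = p0²

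Example: n = 62, r = 3%. p0 = 0.97^62 = 0.151. Exactly one arm: 2 × 0.151 × 0.849 = 26%. Both arms: 0.151² = 2.3%.

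| n per arm in the level | r | p0 | Exactly one arm | Both arms |
|---|---|---|---|---|
| 62 (half of 124) | 3% | 0.151 | 26% | 2.3% |
| 62 | 5% | 0.042 | 8% | 0.2% |
| 62 | 8% | 0.006 | 1% | <0.1% |
| 43 (about 35% of 124) | 3% | 0.270 | 39% | 7.3% |
| 43 | 5% | 0.110 | 20% | 1.2% |
| 43 | 8% | 0.028 | 5% | 0.1% |

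In every row the one-arm case is much the more frequent, so most exclusions would be unnecessary.

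**4. Primary outcome.** With rates of 50% and 30%, a level holding 10% of patients (12 per arm) has p0 = 0.5^12 = 0.0002 and 0.7^12 = 0.0138, so a one-arm zero has probability 1.4%. At 5% of patients (6 per arm) it is 13%. At 20% or more it is about 0.01% or less.

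**5. What does firing do?** Simulations of the infection model (fixed effects only, assumed rates) were run under two sets of assumptions.

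- First set: 124 per arm, 20,000 tables per scenario, rates of 3–5% in one level and 10–20% in the other. With no treatment effect, the type I error was 4.3–4.9% when always adjusting and 4.2–4.7% under the SAP rule. At an odds ratio of 0.4, power was 34.8% against 34.6%, and 43.2% against 42.9%. When the rule fired, the mean SE fell by 0.005 to 0.014, and significance changed in under 1% of fired tables.
- Second set: the rule fired on one arm only in 21–52% of tables, attenuated the log-OR by about 0.01 to 0.10, changed significance in 0.2–4% of fired tables, and cost 0.2 to 2 points of power at an odds ratio of 0.4.

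**The case against.** **The wording has another reading.** The exclusion sentence follows directly on the limit to three or more categories, so its reference to that covariate could carry the limit with it. All but one category is also an odd way to describe one level of two. This stands as an ambiguity, but it does not rescue the rule. On that reading, no listed categorical covariate is covered without a missing-indicator level, and a two-level factor with no events in both arms, where patients really are lost, has no stated remedy.

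**The reach is narrow.** This stands. Myocardial infarction, heart failure, stroke and death get an unadjusted exact regression or no test. Peak troponin is continuous and outside the rule. The primary outcome is exposed only through a very small level. That leaves infection.

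**Stronger inferences that a reader might draw.**

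- *That dropping the factor widens the standard errors.* In these logistic fits the printed SE falls slightly (0.359 to 0.357, and 0.543 to 0.533). An unadjusted analysis after balanced allocation is mildly conservative, but that does not appear as a larger printed SE.
- *That the rule lets the analyst choose covariates after seeing unblinded results.* The rule is fixed in advance and mechanical, and the one discretionary step, merging, is given to a blinded chief investigator. What remains is that the adjustment set depends on outcome by arm where the model does not require it.
- *That the exclusion is always needless.* The trigger also catches a two-level factor with a level empty in both arms, where excluding it is justified.

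**The frequencies rest on assumptions.** This stands too. The SAP gives no infection rate and no split by level, so how often the rule would fire is unknown.

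**Conclusion.** The concern holds as a minor fault. The exclusion trigger does not correspond to the failure that the section sets out to prevent, and the sentence needs rewriting on either reading. That conclusion rests on the form of the models, not on assumed rates.

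The size does depend on assumptions. With 43 to 62 patients per arm in a level and infection rates of 3% to 8% in it, equal in both arms, an unnecessary trigger from that level has probability 1% to 39%, against less than 0.1% to 7% for the case that needs action. When the rule fires, the effect on the infection result is small: slight attenuation of the odds ratio, a slightly conservative test and up to about 2 points of power. The fits and simulations used fixed effects only. The separation argument concerns the fixed part of the model, and failure of the random intercept has its own fallback in the SAP.

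**What to change.** Replace the last sentence of the over-stratification plan, and align the merging sentence with it, for example:

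*A level is merged (three or more categories), or a two-level covariate excluded, only if that level has no events or only events in both treatment groups combined, judged on data pooled over arms; otherwise the minimisation factors stay in the model.*

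This keeps the safeguard where the model needs it, gives two-level factors an explicit rule, and lets the check be made without knowledge of allocation. The cost is one sentence of SAP text. It needs no new data, leaves the sample size unchanged, and has no downside.
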